We will explore the effects of the intervention on patient subgroups defined by factors known or hypothesized to have associations with poorer TBI outcome: facility vs. community discharge, race/ethnicity (White, non-Hispanic Black, Hispanic, Other), age (as continuous), male vs. female, lack of or lower degree of caregiver involvement (yes or no), severity of TBI (moderate vs. severe), presence of pre-injury psychosocial limitations (e.g., unemployment, substance abuse, categorized in yes or no) and medical or psychiatric comorbidity (yes or no), as well as study site, resource variability and insurance type (private insurance vs. Medicaid vs. Medicare). These factors will be entered in a single linear regression model in addition to the intervention group, using PART-O-17 as the response variable. Interactions between each factor and the intervention group will be entered in the model and test of interaction will be the test of heterogeneity. Before constructing the model, we will assess whether the explanatory variables (factors) are correlated to each other.

When two or more variables are deemed highly correlated, to avoid problems with collinearity, we will construct the model with the variable that provides the best model (from fit and diagnostic tests).

From previous research, we hypothesize that severity of TBI and presence of pre-injury psychosocial limitations will interact with the intervention group. With our expected sample size, we anticipate being able to address these questions. Some of the factors might not have a statistically significant effect, but have the effect in the expected direction. Effect sizes and confidence intervals will be calculated to express the potential effect of those factors. The results of these analyses will be valuable in designing future studies.

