Estimated lost to follow up/attrition of patients	Historically, the procedures for participant recruitment and retention used in TBIMS sites has a 90% retention benchmark, and <10% missing data. Given this is a more complex trial requiring increased engagement over time, we anticipate having a more difficult time with retaining participants and therefore are planning for an 80% retention mark.	180
Estimated lost to follow up/attrition of caregivers		110
Estimated monthly enrollment of patients		23-24
Estimated monthly enrollment of caregivers		13-14

Our 80% estimate is based on both our benchmark expectation for enrollment into the TBIMS as well as recruitment rates from the prior intervention studies completed by our team detailed below that have enrolled from the TBIMS population.

Given the broad inclusion criteria and flexibility and provision of treatment that is standard care or higher in both intervention groups, we anticipate meeting our planned recruitment rate.

- (1) The six TBIMS centers in this grant have an average enrollment of 81.35% for TBIMS.
- (2) Bell et al. had a 95% enrollment rate into a single-site study with similar study population and methodology.
- (3) In a multi-site study among 3 TBIMS sites with similar study population and methodology, we had a 90% enrollment rate among those who were eligible.

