### **Power Analysis**

As can be seen in the Recruitment/Enrollment table above (p. 26), we expect to enroll a minimum of 300 individuals per year for 3 years (total N = 900). We based our power calculation on the PART-O-17, the primary outcome for which we have the most relevant data in TBI. Unpublished data from a sample discharged from inpatient TBI rehabilitation showed a PART-O-17 Total (which can range from 0 to 5) average score of 1.51 (SD=0.65) at 3-months follow-up and 1.66 (0.72) at 9-months follow-up (publication in preparation). Minimal detectable differences (MDD) were 0.57 and 0.63 at 3 and 9 months, respectively. Using these results, we calculated the power of finding a difference of 0.60 (average of the two MDDs) between the two groups under various assumptions as follows:

Test: t-test for independent samples, two-tailed, allocation ratio=1

[figure not shown]
Significance level=0.05

Common standard deviations: 0.75 (higher than the observed in previous studies to be conservative)

Mean PART-O scores (Intervention mean minus control mean): The minimal detectable difference of the instrument is 0.6. To be more conservative, we started the difference between the two means at 0.4. Assuming SD=0.75 (in the higher side of previous studies) the calculated effect size based on this mean and SD is 0.5333. Therefore, we used values of 0.5 to 0.8 by increments of 0.05 for the effect sizes.

[figure not shown]
Sample sizes: from 500 to 900 individuals (by 100)

The graph shows that even with an effect size of 0.5 (corresponding to a difference of 0.4 points between the two groups and under an SD larger than those observed in prior studies), we have practically 100% power to detect the difference between the two groups with sample sizes of 500 and above (we expect to have 900).

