When missing values are present we will check the missing mechanism, and if it allows for imputation, we will do so according to the appropriate methods for a continuous variable, using multiple imputation strategies (most likely using maximum likelihood methods). We will perform sensitivity analysis of the results by performing the data analysis using the most conservative approach of removing the data from individuals with missing outcome values from the analysis, or if it a missing value in a covariate, removing the covariate from the model. The results of the analysis with imputed data and complete data will be compared to assess whether they differ and both results will be reported. The analyses for aims related to longitudinal trajectory rely on statistical methods (mixed generalized linear models) that are robust to missing data at individual time points. In addition, all reasons for drop-out and missing data will be recorded and will be reported in all reports and publications (**MD-2, MD-3, MD-5**).

**Plan for analysis of COVID-19 Pandemic impact:** We propose to add the following steps to the data analysis in order to take the pandemic into account: 1) Analyze the patterns and

causes of refusal to participation in the study before and during the pandemic to determine if the populations in the two periods are coming from the same base population; 2) Analyze the patterns of missing data, comparing them between before and during the pandemic to determine whether we need to additionally add an indicator of the time of data collection (before or during pandemic) as another factor in the generation of the imputed outcome data; 3) analyze the primary and secondary outcomes in an intention-to-treat manner as proposed in the protocol. We will follow with another data analysis that will add in the model time of data collection (pre/post pandemic) and its interaction with intervention type as possible explanatory factors to determine the potential impact of change in timing of enrollment or unaccounted for changes in the intervention.

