#### **Analysis of heterogeneity of treatment effects (HT-1, HT-3, HT-4)**

We will explore the differential effects of the intervention on patient subgroups defined by factors known or hypothesized to have associations with poorer TBI outcome: facility vs. community discharge, minority race/ ethnicity, older age, male gender, lack of or lower degree of caregiver

involvement, greater severity of TBI, presence of pre-injury psychosocial limitations (e.g., unemployment, substance abuse) and medical or psychiatric comorbidity, as well as study site, resource variability and insurance type. These factors will be entered in a single linear regression model in addition to the intervention group, using PART-O-17 as the response variable. Before constructing the model, we will assess whether the explanatory variables are correlated to each other. When two or more variables are deemed highly correlated, to avoid problems with collinearity, we will construct the model with the variable that provides the best model (from fit and diagnostic tests). From previous research, we hypothesize that severity of TBI and presence of pre-injury psychosocial limitations will interact with the intervention group, and those interactions will be included in the model. With our expected sample size we anticipate being able to address these questions.

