H3	Monthly SAC Patient and Family AND Quarterly Professional Stakeholder meetings	Include a summary of the monthly SAC patient and family and quarterly professional stakeholder meetings in the interim progress report.	1/31/2021
H	Interim Progress Report Submission	Complete 42-month interim progress report (IPR) and submit via PCORI Online.	1/31/2021
I	Interim Progress Report Submission	Complete 48-month interim progress report (IPR) and submit via PCORI Online.	7/31/2021
J1	IRB Annual Review for lead site (UW)	Submit IRB annual review approval letter to PCORI.	10/31/2021
J4	Complete recruitment	Recruit 900 patient and 540 caregiver participants (100% of total).	10/31/2021
J5	EEF - Schedule and conduct qualitative interviews with stakeholders, staff, investigators	Patient (N~5), family (N~5), professional stakeholders (N~5), study staff and investigators (N~5) interviews completed .	12/31/2021
J6	Annual in-person meeting for patient and family stakeholders and investigators (SAC)	Annual Stakeholder Meeting Include a summary of the discussion in the interim progress report.	12/31/2021
J7	Complete 100% of 3-month follow-ups	Complete 100% of 3-month follow-ups (720 patient and 432 caregiver participants).	1/31/2022
J	Interim Progress Report Submission	Complete 54-month interim progress report (IPR) and submit via PCORI Online.	1/31/2022
K1	Complete 100% of 6-month follow-ups	Complete 100% of 6-month follow-ups (720 patient and 432 caregiver participants).	4/30/2022
K2	EEF - Data analysis complete	Interview data is audio-recorded, transcribed, entered into Dedoose mixed methods software and analysis complete.	6/30/2022

K3	Complete 100% of 9-month follow-ups	Complete 100% of 9-month follow-ups (720 patient and 432 caregiver participants).	7/31/2022
K4	Monthly SAC Patient and Family AND Quarterly Professional Stakeholder meetings	Include a summary of the monthly SAC patient, family and quarterly professional stakeholder meetings in the interim progress report.	7/31/2022
K	Interim Progress Report Submission	Complete 60-month interim progress report (IPR) and submit via PCORI Online.	7/31/2022
L1	IRB Annual Review for lead site (UW)	Submit IRB annual review approval letter to PCORI.	10/31/2022
L2	Complete 100% of 12-month follow-ups	Complete 100% of 12-month follow-ups (720 patient and 432 caregiver participants).	10/31/2022

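### Arm-by-period and arm-by-moderator interactions shrink towards zero if outcomes are imputed without them, and the plan's rule for adding pandemic period does not prevent this

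*Combined protocol and SAP*

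**What the plan says.** The missing-data text in the Data Analysis Plan applies if the missing-data mechanism allows imputation. In that case "we will do so according to the appropriate methods for a continuous variable, using multiple imputation strategies". It does not list what enters the imputation model: arm, moderators, other visits and interactions are all unmentioned. A complete-case analysis is promised as a sensitivity analysis, and both sets of results will be reported.

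The COVID-19 plan in the same section supplies the only explicit rule on what may be added. Step 2 compares missing-data patterns by period "to determine whether we need to additionally add an indicator of the time of data collection (before or during pandemic) as another factor" in generating the imputed outcomes. After the intention-to-treat analyses, step 3 adds a further analysis that will "add in the model time of data collection (pre/post pandemic) and its interaction with intervention type".

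Two sections test moderators. The Heterogeneity of Treatment Effects section says: "Interactions between each factor and the intervention group will be entered in the model and test of interaction will be the test of heterogeneity". It names both primary outcomes in one paragraph and PART-O-17 alone in a later one. The later section, Analysis of heterogeneity of treatment effects, expects that injury severity and pre-injury psychosocial limitations "will interact with the intervention group, and those interactions will be included in the model". None of these sections says whether the interaction tests use imputed or complete-case data.

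**The concern.** A term that will be tested in the analysis model belongs in the imputation model, whether or not missing-data patterns differ by period. Values imputed without an arm-by-period term carry no such interaction, so they dilute the one present in the observed data. Step 2 makes the wrong thing the trigger (a difference in missingness) and offers a remedy (an indicator of period) that does not contain the term step 3 tests. The same applies to any moderator whose interaction with arm is left out.

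The arm-by-period term is the plan's check on whether the pandemic changed the effect of the Rehabilitation Transition Plan (RTP), so a null result will be read as reassurance. Severity and psychosocial limitations are its two hypothesised moderators. A method that pulls these towards no difference works against the purpose of the tests. The planned comparison of imputed with complete-case results could also show a gap caused only by the imputation model.

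**Working it through.** **The plan's own figure.** Table 1 of the recruitment section says the investigators "therefore are planning for an 80% retention mark". 900 × 0.20 = 180 lost, as stated, and 900 × 0.80 = 720 followed, as in the Milestone Schedule. The planned missing share is therefore 20%. The plan states no power for any interaction.

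**Other inputs.** The design is 1:1, two-sided, alpha 0.05. The Milestone Schedule has 360 of 720 six-month follow-ups due by 2/28/2020. The plan gives no cut date, so a pandemic start of about March 2020 and hence a 50:50 period split are assumptions. True interactions of 0, 0.40 and 0.50 SD are also assumptions. Effects are in SD units, so the attenuation ratio does not depend on the scale.

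**Expected shrinkage.** Let δ be the true interaction and m the missing share, equal in all cells. Imputed values from a model without the interaction contribute none, so the completed data show (1 − m) × δ + m × 0.
- m = 10%: ratio 0.90
- m = 20%: ratio 0.80, so 0.40 becomes 0.32
- m = 30%: ratio 0.70

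Now take 10% missing before and 30% during the pandemic. Additive imputation uses a common arm difference that includes 0.7/(0.9 + 0.7) = 0.4375 of δ. The ratio is then 0.70 + (0.30 − 0.10) × 0.4375 = 0.7875.

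**Simulation.** N = 900, normal-model multiple imputation with 20 imputations and Rubin's rules, then regression on arm, period and arm × period, with 500 to 1,000 replicates per scenario. Entries are the mean estimate, with the rejection rate in brackets.

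| True δ, missing | Imputed with arm + period | Imputed with arm × period | Complete cases |
|---|---|---|---|
| 0.50, 10% | 0.457 (0.924) | 0.507 (0.946) | 0.507 (0.946) |
| 0.50, 20% | 0.400 (0.824) | 0.503 (0.910) | 0.501 (0.906) |
| 0.50, 30% | 0.350 (0.646) | 0.501 (0.870) | 0.500 (0.870) |
| 0.50, 10% then 30% | 0.393 (0.802) | 0.500 (0.902) | 0.500 (0.912) |
| 0.40, 20% | 0.320 (0.607) | 0.400 (0.753) | 0.400 (0.756) |
| 0, 20% | −0.004 (0.014) | −0.005 (0.059) | −0.005 (0.058) |

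- The indicator does nothing for this term. At 20% missing and δ = 0.50 the ratio is 0.801 with arm only and 0.800 with arm plus period.
- A second simulation at 20% missing and δ = 0.40 gave about 0.33 with the indicator (power 0.64, size 0.02). With the interaction imputed, or with complete cases, it gave about 0.38 to 0.41 (power 0.73 to 0.77).
- A 75:25 period split at 20% missing gives a ratio of 0.81.
- One correlated other-visit outcome in the imputation (assumed correlation 0.6) raises the ratio to 0.92.
- For a moderator split like facility discharge (22%), with an assumed δ of 0.50 and 20% missing, additive imputation gives 0.40 (power 65%) and imputing within arm gives 0.50 (power 79%).

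**Why the test is conservative.** With arm plus period at 20% missing, the mean Rubin standard error is 0.147 and the empirical SD is 0.121. Under no interaction the approximate size is 2 × [1 − Φ(1.96 × 0.147/0.121)] = 2 × [1 − Φ(2.38)] ≈ 0.017. At δ = 0.40, power ≈ Φ[(0.32 − 1.96 × 0.147)/0.121] = Φ(0.26) ≈ 0.60.

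**Closed-form check of the unattenuated case.** The standard error is 4/√720 = 0.149, and power at 0.40 is Φ(0.40/0.149 − 1.96) ≈ 0.765.

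**The case against.** The strongest reply is that the imputation model is mostly unspecified. Calling the period term an additional factor implies others, unlisted, and imputing by arm or with interactions would fit the wording. The section on replication also assigns missing-data rules to a Manual of Procedures that is not in these documents. This stands: a reader might infer that the plan prescribes additive imputation for every moderator and so biases each test as written, but the documents do not say that. What they do state is the trigger for period and the form it would take, and neither protects the step 3 test.

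Second, no dataset is named for the interaction tests, and a complete-case result is already promised. That also stands: an unattenuated estimate may appear beside an attenuated one. But the plan treats it as a sensitivity analysis, and nothing tells the reader which result answers the interaction question.

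Third, the loss may be smaller. The Data Management section expects rates like 94% completion with under 3% missing PART-O-17. At those limits 1 − 0.94 × 0.97 is about 9% missing, and the ratio is about 0.91. QoLIBRI may fare worse, because proxies do not complete it, but the documents give no figure.

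Fourth, these are exploratory or follow-on tests and type I error is not inflated. That limits the consequence without justifying the rule.

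A reader might also infer that Aim 3 counts will be imputed from a normal model. Around 0.42 hospitalizations per year this would give 26% to 31% negative values: Φ(−0.42/0.648) and Φ(−0.42/0.85). That assumes the method and the SDs, and it uses a rate the plan itself calls rough. The analysis for Aim 1 applies the word continuous to PART-O-17 and QoLIBRI, so the phrase may reach no further.

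**Conclusion.** The concern holds conditionally. The stated rule for pandemic period cannot protect the arm-by-period test, and nothing in the plan protects the arm-by-moderator tests. The shrinkage occurs if outcomes are imputed without the interactions and the tests are run on the imputed data. Under those two conditions the estimate falls by roughly the missing share, and the test rejects a true null in about 1% to 2% of trials instead of 5%. The power loss of about 10 to 15 points is specific to 20% missing, a true interaction of 0.40 SD and an even period split. At 0.50 SD it is about 9 points.

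These figures assume outcomes missing at random given arm and period, and no other-visit outcome in the imputation. Severity and psychosocial limitations were not simulated. The same algebra applies to any two-level moderator with similar missingness across its levels. A wider reading, that the trial's main comparison is compromised, is not supported: neither the primary two-group t-test nor the mixed-model trajectory analyses are shown to be affected.

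**What to change.** - Keep the comparison of missing-data patterns by period as a description, but do not make inclusion of period depend on it.
- Impute PART-O-17 and QoLIBRI separately within each arm, always including pandemic period and the heterogeneity factors. Imputing within arm preserves every two-way arm-by-factor interaction.
- Define period for non-responders by the scheduled assessment date, since they have no date of data collection. This needs a stated calendar cut date.
- State that the interaction tests are reported on both the imputed and the complete-case data.
- Limit the methods for continuous variables to the continuous outcomes. If Aim 3 counts or categories are imputed, use count or ordinal methods, or predictive mean matching.

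The cost is a change of wording in the analysis plan and slightly more parameters per imputation model. About 450 patients are randomised per arm, of whom about 360 would have the outcome at 80% retention (450 × 0.80).

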**Table 1. Recruitment/Enrollment Assessment Timeline**

Begin Recruitment	2/1/18
Recruit 25% of total study participants	11/30/18
Complete 25% of 3-month follow-	2/28/19
Complete 25% of 6-month follow-	5/31/19
Complete 25% of 9-month follow-	8/31/19
Recruit 50% of total study participants	9/30/19
Complete 50% of 3-month follow-	11/30/19
Complete 50% of 6-month follow-	2/28/20
Complete 50% of 9-month follow-	5/31/20
Recruit 75% of study participants	7/31/20
Complete 50% of 12-month follow-	9/30/20
Complete recruitment	10/31/21
Complete 100% of 3-month follow-	1/31/22
Complete 100% of 6-month follow-	4/30/22
Complete 100% of 9-month follow-	7/31/22
Complete 100% of 12-month follow-	10/31/22
Primary Completion Date	10/31/22

Targeted total participant enrollment N	900
Targeted total caregiver enrollment N	540
Number of sites	6
Site Names	

- University of Washington

- Indiana University School of Medicine/Rehabilitation Hospital of Indiana

- Einstein Healthcare Network / Moss Rehab Hospital

- Baylor Institute for Rehabilitation

- Ohio State University Wexner Medical Center

- Mount Sinai Health System (NY)

Estimated patient volume	In 2015, 764 individuals with TBI were discharged from inpatient rehabilitation across the six study sites. In 3 years of recruitment in our study, a conservative estimate for screening would be approximately 2200 individuals
Estimated number of eligible patients	Of those discharges in 2015, 430 (56%) would meet the eligibility criteria for the TBIMS as described in the Research Plan inclusion/exclusion criteria. We would expect
	1230

that approximately 1230 (about 56%) would be eligible for our study.		
Estimated number of eligible caregivers		600
Estimated yield/consent of patients	Enrollment rate for the six sites was 81% from October 2015 through October 2016. In 2015, 345 individuals who had a TBI and were eligible enrolled into the TBIMS across the 6 study sites. Over 3 years of enrollment, we conservatively estimate that at least 900 (73% of the eligible) participants will consent to enroll into our study.	900
Estimated yield/consent of caregivers		540

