#### *Discharge Information: Patient Participants*

Research staff will collect information from a patient participant's medical record regarding the presence/absence of recommended and/or scheduled appointments to different medical disciplines/services as well as documenting received/recommended equipment using the *BRITE Study Discharge Information* data collection form. These data will be entered into the NDSC centralized database by research staff. Specific information regarding the

recommended/scheduled appointments (e.g. name, phone number, email address, date of scheduled appointment, etc.) of patient participants randomized to the RTP intervention arm will be stored locally in a database used by the TBI care managers for referential purposes.

Research staff will also enter discharge destination and date as well as injury date into the NDSC database using the *BRITE Study Discharge Destination and Date* data collection form

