#### *Other Components of RTP*

We will include several other components of the RTP condition to help establish continuity of care and to provide a "safety net" for patients experiencing problems between calls.

- A Follow-up letter will be sent by post or electronically (email, text) immediately after each scheduled contact summarizing the discussion points and mutually agreed-upon plans.
- A final letter will be sent to the patient and/or caregiver participant following the end of the RTP phase that provides a summary of the follow up plan, a list of resources provided during the contacts, and any reminders/suggestions/strategies moving forward.
- In addition, with the participants' permission, a letter may be sent to a primary care provider or other relevant provider after completion of the RTP phase to assist with coordination of care, provide updates, and explain participant has concluded study participation.
- Based on feedback from our stakeholders, we will provide a telephone number staffed by the TCM during business hours to all patients/ families in the RTP group as well as others involved in their care so that they may contact the TCM between regularly scheduled calls.  
*"A week for the introductory call is fine as long as we send them home with a telephone number to call in case something comes up sooner. A week can feel like a year when you need help."* (Family Stakeholder).

- The TCM will also be available during business hours via e-mail or text message. Reminder email or text messages may be sent by the TCM to patient or caregiver participants to remind of appointments or follow-up plans as requested

The TCMs will attempt to reach participants to complete the RTP scheduled contacts until: 1) a planned number of contacts have been completed, 2) the participant declines or is deemed unable to complete the RTP contacts (withdrawal, death, etc.), or 3) the RTP window expires six months following discharge. The TCMs will strategize with their supervisors ways to manage participants that are difficult to reach on a case-by-case basis. In addition, TCMs may send a letter to both patient and caregiver participants indicating that they have been unable to reach them and request the participant contact research staff to arrange for upcoming contacts.

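### The supplementary COVID-19 model uses collection date to answer a question about enrolment and delivery timing, which dilutes its interaction with arm, most of all at 12 months

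*Combined protocol and SAP*

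**What the plan says.** The COVID-19 paragraph in *Data Analysis Plan Specific to Each Aim* has three steps.

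1. Compare patterns and "causes of refusal to participation in the study before and during the pandemic".
2. Compare missing-data patterns between the two periods and decide from that whether to "add an indicator of the time of data collection (before or during pandemic) as another factor in the generation of the imputed outcome data".
3. Run the intention-to-treat analyses of primary and secondary outcomes as already planned, then a further analysis that will "add in the model time of data collection (pre/post pandemic) and its interaction with intervention type as possible explanatory factors". Its purpose is "to determine the potential impact of change in timing of enrollment or unaccounted for changes in the intervention".

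No calendar date for the start of the pandemic is given.

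Other sections bear on this. *Scheduling of Contacts* has RTP contacts beginning one week after discharge, and under *Other Components of RTP* "the RTP window expires six months following discharge". Under *Discharge Information*, "Research staff will also enter discharge destination and date as well as injury date into the NDSC database". Randomization comes after discharge. Aim 1 compares the arms at 6 months (primary) and again at 12. *Questionnaire Scheduling and Timing* lets the 6-month questionnaire run from 15 days early to 30 days late, and the 12-month one up to two months either way, with a two-week extension in some cases.

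**The concern.** The variable and the question do not match. Enrolment timing, and whether the intervention was delivered in the pandemic, are settled by discharge date and the six months that follow. Collection date is later than both by the length of follow-up. A patient discharged before the pandemic can therefore carry a pandemic label, and at 12 months can carry it after finishing RTP or the RDP comparison period before the pandemic began. Step 1 does use enrolment-side timing, but only for refusals, not for the treatment effect.

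Three lesser points follow from the same choice. Collection date is set after randomization and depends partly on how easily a patient is reached, whereas discharge date precedes randomization. A missed questionnaire has no collection date, and the plan does not say which date stands in for it. A first-year utilization total (Aim 3) is built from four questionnaires and has no single collection date.

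At stake is the one planned check on whether the RTP effect differed in the pandemic. If that check is diluted, finding no interaction is easily read as more reassurance than it gives.

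**Working it through.** The plan states no figure for this analysis, so there is none to reproduce. The check maps planned accrual onto the calendar.

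**Inputs.** Table 1 and the Appendix 1 milestones: recruitment starts 2/1/18; 225 patients by 11/30/18, 450 by 9/30/19 (the row "Recruit 50% of total study participants"), 675 by 7/31/20, 900 by 10/31/21. Intervention period: six months from discharge. Planned retention: 80%, so 720 assessed. Alpha 0.05, allocation 1:1.

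**Assumptions.** Linear accrual between milestones; enrolment close to discharge; pandemic start 15 March 2020, varied from 1 March to 1 April.

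**Step 1: by enrolment.** 30 September 2019 to 15 March 2020 is 167 of the 305 days in that accrual segment. Before: 450 + 225 × 167/305 ≈ 573. During: 900 − 573 = 327.

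**Step 2: by 6-month collection date (ideal date).** Collection before the cut needs discharge by mid-September 2019, about 288 of the 304 days after 30 November 2018. Pre: 225 + 225 × 288/304 ≈ 438. During: 462. Enrolled before but labelled *during*: 462 − 327 = 135, which is 15% of 900 and 29% of 462. All 135 had part of their six months after the cut.

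**Step 3: by 12-month collection date.** Discharge by mid-March 2019, about 105 of 304 days. Pre: 225 + 225 × 105/304 ≈ 303. During: 597. Enrolled before but labelled *during*: 597 − 327 = 270, which is 30% of 900 and 45% of 597. Of these, 438 − 303 = 135 had their whole six months before the cut.

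Counts cover both arms. The error runs one way: no patient enrolled in the pandemic is labelled *pre*.

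**Step 4: dilution.** Fraction of the interaction kept = mean true exposure in *during* minus mean in *pre* (the latter is 0 here).

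| True modifier | 6 months | 12 months |
|---|---|---|
| Enrolment period | 327/462 = 0.71 | 327/597 = 0.55 |
| Share of six months after the cut (straddlers average about ½) | (327 + 67.5)/462 = 0.85 | (327 + 67.5)/597 = 0.66 |
| Share of 12 contacts (assumed at weeks 1, 2, 3, 4, 6, 8, 10, 12, 14, 18, 22, 26) | 0.82 | 0.64 |

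**Step 5: precision.** In SD units, SE = √[4/(np) + 4/(n(1−p))] with n = 720; detectable at 80% power = (1.960 + 0.842) × SE.

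| Split | p during | SE | Detectable |
|---|---|---|---|
| 6-month collection | 462/900 = 0.513 | 0.149 | 0.42 |
| 12-month collection | 597/900 = 0.663 | 0.158 | 0.44 |
| Discharge before/after | 327/900 = 0.363 | 0.155 | 0.43 |

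Allowing for dilution, the true interaction must be 0.42/0.85 = 0.49 to 0.42/0.71 = 0.59 SD at 6 months, and 0.44/0.66 = 0.67 to 0.44/0.55 = 0.80 SD at 12, to be detected with 80% power. For scale, the revisited power analysis considers main effects from 0.3 SD.

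**Sensitivity** to start date and to assessment anywhere in its window (including the extension at 6 months): 123–168 patients discordant at 6 months (27–35% of *during*) and 225–315 at 12 months (40–50%), of whom 90–180 had the whole period before the cut.

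**The case against.** The strongest reply concerns the primary endpoint. The 6-month assessment falls at the end of the RTP window, so at the ideal date a *during* label means exactly that some of the window lay in the pandemic. The label merges straddlers with later patients, which is coarse, but it does not misplace people whose intervention was over. Only late assessment breaks the match: 22–33 patients if everyone were assessed 30 to 44 days late. This stands, and it confines the clear misplacement to 12 months.

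Second, a reader might infer that the model cannot answer its question. The documents do not support that. The *pre* group is clean, most *during* patients are correctly placed, and most of the 6-month interaction survives.

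Third, collection date is the right variable for a different mechanism. PART-O-17 covers productivity, social relations and being out in the community, which the pandemic could alter at the moment of measurement. If that is the modifier, there is no dilution. RTP was mainly by telephone already, and Appendix 3 says remote delivery left the study well placed to continue. This stands as a reason to keep assessment period, not to leave out discharge period: the plan's stated question names enrolment and intervention changes.

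Fourth, a reader might infer that the imputation step cannot be run. It can. Comparing missingness before and during the pandemic already implies dating missed assessments by when they were due; that date follows from discharge date; and adding the indicator is conditional. What remains is an unstated definition.

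Finally, the drift and utilization points are small. A started questionnaire keeps its start date, so the extension moves few dates. Utilization is gathered at four dated questionnaires, and in the Aim 2 and 4b mixed models the term can vary by assessment.

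**Conclusion.** The concern holds as a mismatch between variable and stated question in a supplementary analysis. If enrolment or delivery period is the true modifier, the interaction is diluted moderately at 6 months and heavily at 12. Across the start dates and assessment windows tried, the fraction kept is 0.65–0.73 (enrolment) or 0.79–0.88 (share of the period) at 6 months, and 0.50–0.60 or 0.61–0.72 at 12. A null interaction is then weak reassurance, particularly at 12 months.

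The intention-to-treat t-test at 6 months is untouched unless the indicator is brought into the imputation model.

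The counts rest on target accrual, enrolment close to discharge and an assumed start date. A slowdown in recruitment after March 2020 would change them; the direction of the error would not change.

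**What to change.** In the COVID-19 paragraph:

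- State the calendar cut date.
- Add a discharge-based period with three levels (six-month window ended before the cut; straddled it; discharged after it) and its interaction with arm, as the modifier for the stated question. It is fixed before randomization and is defined once per patient, so it also serves the first-year utilization totals.
- Keep assessment period, dated by the scheduled assessment, for the pandemic's effect at the time of measurement. At 12 months and in the longitudinal models it can sit beside the discharge period. At 6 months the two cannot both be fitted: the scheduled date falls after the cut exactly when the window has not ended before it, so assessment period is the straddled and after groups combined. Run it there as a sensitivity analysis.
- Use the scheduled date (discharge plus 3, 6, 9 or 12 months) for the missing-data comparison and any imputation.

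The cost is a few sentences and no new data. A two-level discharge split has almost the same precision as the 6-month collection split (0.43 against 0.42 SD). Three levels, and collinearity with assessment period where both are fitted, will make individual contrasts less precise; that is acceptable in a supplementary analysis.
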